## **Study Protocol and Statistical Analysis Plan with Results**

A total of 69 patients with uncontrolled open-angle glaucoma were recruited at the George Washington University by two glaucoma attending professors. Research protocol approval was obtained from the institutional review board of George Washington University (Washington, DC, USA) under IRB #041, 310 and registered on ClinicalTrials.gov with identifier NCT01956942. Written informed consent was received from all patients, and the protocol followed the Declaration of Helsinki.

This study included all laser trabeculoplasty candidates with open-angle glaucoma on maximally tolerated medical therapy with the need for additional IOP lowering. Patients with end-stage, neovascular, uveitic, or angle closure glaucoma were excluded. In all, 38 patients were randomized to MLT and 31 patients to SLT via a random number generator protocol approved for up to 100 patients. All patients had only one eye included in the study. Patients were allocated to each group without any stratification based on prior characteristics via sealed numbers in a set sequence. Recruitment was concluded after a power analysis revealed an 80% power at a 0.05  $\alpha$  level detecting an average 2.99 mmHg or 16.19% decrease from baseline between the SLT and MLT groups. This level was determined based on prior studies defining a \$3 mmHg or \$20.0% decrease in IOP as a significant difference from baseline.11 Patients, physicians, and researchers were not blinded to the different laser treatments. Each of the two physicians performed both the laser treatments and all subsequent follow-ups for a particular patient.

The MLT group underwent 360° treatment with the IQ 577 nm™ yellow laser (Iridex Corporation, Mountain View, CA, USA) with laser applied to the pigmented trabecular meshwork in a confluent manner. The laser settings for MLT were 1,000 mW, 300 ms duration, 300 µm spot size, and a 15% duty cycle. The SLT group received 360° treatment with the 532 nm Q-switched, frequencydoubled Nd:YAG Selecta II™ (Lumenis Inc, San Jose, CA, USA). The energy for SLT was titrated, between ~0.6 and ~2.0 mJ, based on trabecular meshwork pigmentation to achieve a noticeable gas bubble response, utilizing a 400 µm spot size and a 3 ns duration.

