All patients were treated with one drop of apraclonidine prior to the treatment. Patients were discharged with topical diclofenac 0.1% to use as needed for discomfort. At week 1, patients completed a standardized survey querying discomfort experienced both during and after the procedure and use of the topical diclofenac.

Patients' IOP was measured at predefined intervals of 1 hour and 1-, 6-, 6–12-, 12–24-, 24–36-, and 36–52-week intervals based on a fixed follow-up of 1 and 6 weeks and a tendency to follow these patients every 3–4 months thereafter. Pretreatment IOP values were calculated as the average of up to three preceding visits to reduce fluctuations. Only the preceding visits without the addition of a drop or a laser were included to avoid confounding influences. If patients were examined multiple times within an interval, IOP values were averaged for statistical analysis. Patients' responses were excluded from the analysis if they underwent any interventions that may affect their IOP, including the addition of a topical antihypertensive drop, cataract surgery, cyclophotocoagulation, incisional glaucoma surgery, or further laser trabeculoplasty. However, their data were still included for the intervals up to the time of these interventions. Comparison between groups was calculated with Student's *t*-test for continuous data and a two-tailed Fisher's exact test for categorical data.

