## Results

There was no statistically significant difference in demographic characteristics between groups, as seen in Table 1. The MLT patients had a higher average starting IOP (18.26 mmHg) than the SLT group (16.85 mmHg), approaching significance (P=0.08). Both groups had very similar 1 hour posttreatment IOP, 15.15 mmHg in the MLT group and 15.65 mmHg in the SLT group. An IOP spike was defined as an elevation of .5 mmHg from the pretreatment mean. Incidence of post-procedure spikes were 5.3% and 12.9% in the MLT and SLT groups, respectively, but this difference was not statistically significant (P=0.4). No group experienced any anterior chamber inflammation upon examination at the 1 week follow-up time point.

Follow-up data at the 1-, 1–6-, 6–12-, 12–24-, 24–36-, and 36–52-week intervals were tabulated as absolute IOP decreases from pretreatment levels (Figure 1) and percentage IOP decreases from baseline (Figure 2). These data demonstrated that both MLT and SLT provided comparable decreases in IOP from baseline as both an absolute measurement and a percentage decrease at all intervals up 52 weeks (*P*.0.05). In addition, the confidence intervals at each time period were, 3 mmHg when viewed as an absolute decrease in IOP and, 20.0% when viewed as a percentage decrease from baseline IOP, except one outlier interval (week 24–36 in Figure 1). A Kaplan–Meier curve is demonstrated in Figure 3. As expected, the larger proportion of failures in the MLT group produced a lower curve, with more of the MLT failures occurring in the early period. However, the survival curve steps in both groups were similar at later intervals, leading to a log-rank *P*-value of 0.31.

The data from the standardized pain survey (scale of 0= none to 10= severe) revealed that the MLT patients experienced a mean 1.34/10 during treatment and 0.89/10 during the 1 week posttreatment period, while the SLT patients noted 2.83/10 during treatment and 2.81/10 during the 1 week posttreatment period. The MLT patients on average experienced less pain both during and after the treatment (P=0.005).

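### Late mean-IOP comparisons use only patients not yet given further treatment; removal was more frequent and earlier in MLT, so later contrasts are probably tilted modestly in MLT's favour

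*Combined protocol and SAP*

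**What the plan says.** The methods text (section Study Protocol and Statistical Analysis Plan with Results) sets the rule: "Patients' responses were excluded from the analysis if they underwent any interventions that may affect their IOP". The listed interventions are an added pressure-lowering drop, cataract surgery, cyclophotocoagulation, incisional glaucoma surgery and repeat laser. Readings before the intervention are kept: "However, their data were still included for the intervals up to the time of these interventions".

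On the test: "Comparison between groups was calculated with Student's *t*-test for continuous data and a two-tailed Fisher's exact test for categorical data". No longitudinal model, imputation or sensitivity analysis is described.

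The Results give the IOP comparison interval by interval and conclude that "both MLT and SLT provided comparable decreases in IOP from baseline as both an absolute measurement and a percentage decrease at all intervals" up to 52 weeks, with P above 0.05 throughout. The confidence intervals are said to stay below 3 mmHg or 20%, except for absolute IOP at weeks 24–36.

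Failures are reported separately: 23.7% in MLT and 12.9% in SLT, a Kaplan–Meier curve with log-rank P = 0.31, and the remark on timing "with more of the MLT failures occurring in the early period".

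**The concern.** A t-test within one interval uses only the readings in that interval. A patient who did poorly at week 6 and was then given a drop counts in the early means and is absent from every later one; the week-6 reading does not inform the later estimate. The test therefore treats the remaining patients as a random sample of their arm.

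That is doubtful here, because the Results treat further glaucoma treatment as evidence that the laser had failed. Removing failures raises the late mean decrease in both arms, and raises it more in the arm that loses more patients. That arm is MLT, and its failures came earlier, so they are missing from more of the intervals. The claim at stake is comparability of mean IOP decrease out to 52 weeks. No primary endpoint is named; this is the comparison the Results report first for follow-up.

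**Working it through.** **1. Inputs from the document.** "In all, 38 patients were randomized to MLT and 31 patients to SLT". Failures of 23.7% and 12.9% correspond to 9/38 and 4/31. Starting IOP was 18.26 mmHg (MLT) and 16.85 mmHg (SLT), P = 0.08.

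**2. How many patients remain late.** The numbers per interval are in figures that were not available. The 24–52-week success percentages give them indirectly. Within the arm sizes, 29.6% and 37.0% both fit only n = 27 (8/27 and 10/27), and 36.0% fits only n = 25 (9/25).
- Fisher's exact test, 8/27 v 9/25: P = 0.77, as stated.
- Fisher's exact test, 10/27 v 9/25: P = 1.0, as stated.

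So 38 − 27 = 11 MLT patients (29%) and 31 − 25 = 6 SLT patients (19%) are absent. Failures can explain at most 9 and 4 of these. A patient who failed late may still have contributed a reading to this period, so 9 and 4 are upper limits.

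**3. Precision of the imbalance.** Difference 0.2368 − 0.1290 = 0.108. SE = √(0.2368 × 0.7632/38 + 0.1290 × 0.8710/31) = 0.0915. The 95% interval is 0.108 ± 0.179, about −7 to +29 percentage points.

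**4. Formula for the tilt.** Let p be the share of an arm removed and d the mean decrease in retained patients minus that in removed patients. The retained mean exceeds the full-arm mean by p × d, so

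tilt toward MLT = p(MLT) × d(MLT) − p(SLT) × d(SLT).

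The document gives no value for d. Taking the largest possible p (9/38 and 4/31):

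| d in MLT | d in SLT | Tilt toward MLT (mmHg) |
|---|---|---|
| 1 | 1 | 0.108 × 1 = 0.11 |
| 3 | 3 | 0.108 × 3 = 0.32 |
| 5 | 5 | 0.108 × 5 = 0.54 |
| 5 | 0 | 0.2368 × 5 = 1.18 |
| 2 | 5 | 0.474 − 0.645 = −0.17 |

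With equal d the tilt favours MLT. With unequal d it can be larger, or reverse.

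**5. A value for d from an assumed removal rule.** All settings here are assumptions: between-patient SD 2.6, response SD 2.5, visit SD 2 mmHg, six post-treatment readings, and removal after any reading above 21.5 mmHg.
- *Common baseline 17.6; mean decrease 1.0 (MLT) v 2.5 (SLT).* Removed before the last interval: 25% v 14%. True contrast −1.51; contrast in retained patients −1.25; tilt 0.26. Here d is 2.7 and 3.0, and the formula agrees: 0.252 × 2.73 − 0.145 × 2.96 = 0.26.
- *Documented baselines 18.26 and 16.85; equal mean decrease of 2.0.* Removed: 22% v 13%, close to the reported 23.7% v 12.9%. True contrast 0; contrast in retained patients +0.22; tilt 0.23.

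**6. Does using the earlier readings help?** In a simulation with the first set of assumptions plus 15% random late loss, the true contrast was −1.52. The interval contrast averaged −1.24, and a likelihood analysis of the same pre-intervention readings −1.49. Empirical standard errors at 38/31 were 0.97 and 1.02.

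**The case against.** **The gain is small at this sample size.** From step 6, root mean squared error is √(0.28² + 0.97²) = 1.01 for the interval t-test and √(0.03² + 1.02²) = 1.02 for the model. This stands: the model does not bring the estimate closer to the truth on average. It does remove an error of predictable direction, which matters when the conclusion is that two treatments are alike.

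**The imbalance in failures need not mean that MLT works less well.** This also stands. With the documented baselines and identical response, a fixed IOP threshold alone produces nearly the reported failure rates. The tilt of about 0.23 mmHg remains in that case, but there is then no deficit to conceal. Any model should therefore adjust for baseline IOP.

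**The failures are disclosed.** The failure proportions by type and the Kaplan–Meier curve show the imbalance openly. They do not correct the IOP means beside them.

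**Poor response among removed patients is inferred.** No IOP at the time of intervention and no threshold for intervening is given, the physicians were unblinded, and cataract surgery need not reflect poor control. The inference is reasonable for the counted failures, which were all further glaucoma treatment, but it remains an inference.

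**Stronger readings.** A reader might infer that the late means hide a real MLT deficit, or that comparability would fail on reanalysis. The documents support neither: no true deficit is known, and with equal d the tilt would reach 3 mmHg only at d = 3/0.108, about 28 mmHg. A reader might also take d as 3–6 mmHg and quote 0.32–0.65 mmHg. That uses the maximum removal counts, and the assumed removal rule gives d of only about 3.

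**Conclusion.** The concern holds as a tilt. Late interval comparisons are made in unequally selected patients, with up to 9/38 removed in MLT and 4/31 in SLT and the MLT removals earlier. If removed patients had smaller decreases, by a similar amount in both arms, the late contrasts lean toward MLT and understate any MLT deficit.

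The actual size cannot be estimated without the interval means, SDs and counts. Under an IOP-triggered removal rule it is roughly 0.2–0.3 mmHg. That is about a quarter to a third of the simulated standard error, and far below 3 mmHg. It does not overturn the reported result. It does mean that comparability at the later intervals should not rest on unadjusted t-tests alone, particularly as the confidence interval at weeks 24–36 already passes the 3 mmHg mark.

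**What to change.** - Replace the separate interval t-tests with one mixed model for repeated measures. Use all pre-intervention readings of all 69 randomised patients, with arm, interval, arm-by-interval, baseline IOP and baseline-by-interval. Report the arm contrast with its 95% CI at 36–52 weeks.
- Use an unstructured within-patient covariance. Six intervals need 6 × 7/2 = 21 covariance parameters from 69 patients, so state a simpler structure in advance in case the model does not converge.
- Add one sensitivity analysis for non-random removal, such as multiple imputation with the imputed decreases of failed patients reduced by a stated range of amounts. Carrying the last value forward is not a good substitute, because single imputation understates the variance.
- Give the number analysed per arm at each interval, and state beside the mean IOP results that late means exclude patients who failed.

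The cost is statistician time and wording; no new data are needed. The standard error rises slightly (1.02 v 0.97 mmHg in the simulation). The model also assumes that baseline and earlier readings explain who was removed, which the sensitivity analysis is there to test.

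### The pooled-variance t-test suits the 0–10 pain scores poorly, and P=0.005 for the trial's only significant difference is probably somewhat too small

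*Combined protocol and SAP*

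**What the plan says.** The methods text under the title heading gives one rule for every continuous outcome: "Comparison between groups was calculated with Student's *t*-test for continuous data". Two-tailed testing is stated only for the categorical comparison ("a two-tailed Fisher's exact test for categorical data"). The text does not say whether the t-test pools variances. It names no variance check, unequal-variance option or rank-based alternative.

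On allocation it says that "38 patients were randomized to MLT and 31 patients to SLT".

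The Results section describes a "standardized pain survey (scale of 0= none to 10= severe"). For the MLT arm it gives "a mean 1.34/10 during treatment and 0.89/10 during the 1 week posttreatment period". The corresponding SLT means are 2.83 and 2.81. One P value covers both comparisons: "The MLT patients on average experienced less pain both during and after the treatment (P=0.005"). No SD, interval, t statistic or number of respondents is given for either pain score.

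**The concern.** On a scale that stops at 0, a mean close to 0 leaves little room for spread. The MLT means are roughly a half and a third of the SLT means, so the MLT variance is likely to be the smaller one. A pooled test assumes the two are equal. When the larger variance lies in the smaller arm, pooling gives too much weight to the less variable arm, and the standard error comes out too small.

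Pain is the only between-group comparison that the document reports as significant. The other P values are 0.08 (baseline IOP), 0.4 (spikes), above 0.05 (IOP at all intervals), 0.31 (log-rank), 0.77 and 1.0 (response) and 0.22 (failures). What is at stake is the standard error, interval and P value of the one positive comparative claim.

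**Working it through.** **Inputs.** From the documents: arms of 38 and 31; means 1.34 v 2.83 (during) and 0.89 v 2.81 (after); P=0.005; scale 0–10. Assumed: the test was pooled and two-sided, and all 69 patients answered.

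**Step 1: the stated P value.** Without SDs, P=0.005 cannot be reproduced forward. It can only be solved backwards. With 38 + 31 − 2 = 67 degrees of freedom, two-sided P=0.005 needs t = 2.903. The factor √(1/38 + 1/31) is 0.2420.

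- After treatment: difference 2.81 − 0.89 = 1.92; SE = 1.92/2.903 = 0.661; pooled SD = 0.661/0.2420 = 2.73. Rounding of P (0.0045 to 0.0055) moves this only between 2.70 and 2.76.
- During treatment: difference 2.83 − 1.34 = 1.49; SE = 1.49/2.903 = 0.513; pooled SD = 0.513/0.2420 = 2.12.

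**Step 2: the largest SD the MLT mean allows.** On 0–10 with mean m, the largest sample SD is √(m(10 − m)·n/(n − 1)), reached when all scores are 0 or 10.

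- After: √(0.89 × 9.11 × 38/37) = 2.89. The implied 2.73 is 2.73/2.89 = about 95% of it.
- During: √(1.34 × 8.66 × 38/37) = 3.45. The implied 2.12 is 2.12/3.45 = about 61% of it.

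For the after score, 38 whole-number scores averaging 0.89 reach such an SD only in extreme patterns. Three patients at 10, one at 4 and 34 at 0 give 2.78. A still very skewed set (10, 8, 6, 5, 5 and 33 zeros) gives 2.44. Equal variances are therefore implausible for the after score if P=0.005 is its P value. For the during score they remain possible.

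**Step 3: the effect of not pooling.** Hold the pooled P at 0.005. For an assumed MLT SD s₁, the SLT SD s₂ follows from 37s₁² + 30s₂² = 67 × 2.73². The Welch SE is √(s₁²/38 + s₂²/31). For the after score (pooled SE 0.661):

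| MLT SD | SLT SD | Ratio | Welch SE | Pooled SE too small by | Welch P |
|---|---|---|---|---|---|
| 2.44 | 3.06 | 1.25 | 0.677 | 2% | 0.006 |
| 2.0 | 3.4 | 1.7 | 0.696 | 5% | 0.008 |
| 1.5 | 3.7 | 2.5 | 0.713 | 7% | 0.010 |
| 1.0 | 3.9 | 3.9 | 0.724 | 9% | 0.012 |

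With the pooled P fixed, Welch P depends only on the SD ratio and the arm sizes, so the during score gives the same values at the same ratios. At a ratio of 10, Welch P is 0.0135. At the reversed ratio of 0.5 it is 0.0031.

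**Step 4: error rate.** In 100,000 simulated trials per setting, with normal data and 38 v 31 patients, the pooled test at nominal 0.05 rejected a true null in 5.9%, 6.6% and 7.5% of runs for SLT/MLT SD ratios of 1.5, 2 and 3. Welch's test stayed between 4.9% and 5.1%.

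**Step 5: dependence on who answered.** Taking SD proportional to the mean and pooled P at 0.005, Welch P (during, after) is 0.0096 and 0.0115 at 38/31, 0.0056 and 0.0061 at 31/31, and 0.0042 and 0.0043 at 28/31. The count matters because 2.83 cannot be the mean of 31 whole-number scores (87/31 = 2.81, 88/31 = 2.84), although 85/30 and 82/29 both round to 2.83. If scores were whole numbers, some answers are probably missing.

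**The case against.** A reader might infer that the trial's own figures prove the reported P value too small. They do not. Every SD above is solved back from one rounded P value that covers two comparisons. If it belongs to the during score, equal variances fit comfortably. The SDs implied for the after score are themselves strained: SLT SDs of 3.4 to 3.9 are 75–86% of the maximum of 4.57 at a mean of 2.81. That may mean that P=0.005 is not the after-score P at all. If the after score had an SD of 2.12, its pooled P would be about 0.0004, and its Welch P at a 3:1 SD ratio about 0.0015, both below the printed value. The documents cannot settle this, and they do not rule out that the software's unequal-variance option was used. These objections stand. They make the bias a likely inference and not a demonstrated error.

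A reader might also infer that the pain result loses significance, or that the IOP comparisons are affected too. Neither is supported. No ratio examined brings P near 0.05, and nothing in the documents shows a variance problem for IOP.

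It is also fair to say that unblinded self-report, and one P value for two scores, are larger threats to the pain result than pooling.

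What the objections do not remove is the choice of test. With floor-limited scores, means two to three times apart and unequal arms, the likely direction of error is known, and a test that avoids it is available at almost no cost.

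**Conclusion.** The point holds as a minor one. Pooling is a poor choice for these scores. Equal variances are implausible for the after score if P=0.005 belongs to it and all 69 answered; for the during score inequality is likely but unproven. For SLT/MLT SD ratios from 1.25 to 3.9, the pooled standard error is about 2–9% too small, and P=0.005 becomes about 0.006–0.012. The conclusion at the 0.05 level does not change. The size rests on a pooled, two-sided test, 38 and 31 respondents, and the larger variance lying in the SLT arm. With equal numbers of respondents the effect nearly vanishes, and with fewer MLT than SLT respondents it can reverse.

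**What to change.** In the statistical methods text, name Welch's unequal-variance t-test for the two pain scores as the governing analysis, with a rank-sum or permutation P value as a sensitivity analysis only. The test for the IOP outcomes need not change on this ground.

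In the Results paragraph on the pain survey, report for each score separately: respondents and SD by arm, the mean difference, its Welch 95% interval and its own P value. State that the change was made after the results were known. These figures would also show which comparison P=0.005 refers to.

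The cost is a short change of wording and a re-run on existing data, with a slightly larger P value the likely result.

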## Results

There was no statistically significant difference in demographic characteristics between groups, as seen in Table 1. The MLT patients had a higher average starting IOP (18.26 mmHg) than the SLT group (16.85 mmHg), approaching significance (P=0.08). Both groups had very similar 1 hour posttreatment IOP, 15.15 mmHg in the MLT group and 15.65 mmHg in the SLT group. An IOP spike was defined as an elevation of .5 mmHg from the pretreatment mean. Incidence of post-procedure spikes were 5.3% and 12.9% in the MLT and SLT groups, respectively, but this difference was not statistically significant (P=0.4). No group experienced any anterior chamber inflammation upon examination at the 1 week follow-up time point.

Follow-up data at the 1-, 1–6-, 6–12-, 12–24-, 24–36-, and 36–52-week intervals were tabulated as absolute IOP decreases from pretreatment levels (Figure 1) and percentage IOP decreases from baseline (Figure 2). These data demonstrated that both MLT and SLT provided comparable decreases in IOP from baseline as both an absolute measurement and a percentage decrease at all intervals up 52 weeks (*P*.0.05). In addition, the confidence intervals at each time period were, 3 mmHg when viewed as an absolute decrease in IOP and, 20.0% when viewed as a percentage decrease from baseline IOP, except one outlier interval (week 24–36 in Figure 1). A Kaplan–Meier curve is demonstrated in Figure 3. As expected, the larger proportion of failures in the MLT group produced a lower curve, with more of the MLT failures occurring in the early period. However, the survival curve steps in both groups were similar at later intervals, leading to a log-rank *P*-value of 0.31.

The data from the standardized pain survey (scale of 0= none to 10= severe) revealed that the MLT patients experienced a mean 1.34/10 during treatment and 0.89/10 during the 1 week posttreatment period, while the SLT patients noted 2.83/10 during treatment and 2.81/10 during the 1 week posttreatment period. The MLT patients on average experienced less pain both during and after the treatment (P=0.005).

Prior authors defined a successful laser trabeculoplasty as \$3 mmHg IOP decrease or \$20.0% IOP decrease from baseline.6,8 Using these criteria, 29.6% of the MLT and 36.0% of the SLT patients experienced a 20.0% IOP decrease from baseline during the 24–52-week interval (P=0.77). Similarly, 37.0% of the MLT patients and 36.0% of the SLT patients experienced a \$3 mmHg IOP reduction from baseline at the 24–52-week interval (P=1.0).

Patients in each group were also assessed to determine the proportion that required further intervention for their glaucoma during the 52-week follow-up period, indicating a failure of the laser therapy. In the MLT group, a total of 23.7% of patients failed and required further treatment for their glaucoma. A topical antiglaucoma agent was added in 15.8% of the MLT patients, incisional glaucoma surgery was performed in 2.6% of the MLT patients, and transscleral cyclophotocoagulation was performed in 5.3% of the MLT patients. In the SLT group, 12.9% of the patients failed, with all the failures due to the addition of another topical antiglaucoma medication. Although there were a greater number of failures in the MLT group (23.7%) compared to the SLT group (12.9%), the analysis did not meet significance in each individual category or when considered in sum (P=0.22). No patient in either group experienced any complications, other than a transient rise in IOP.

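### IOP decreases are compared by unadjusted t-test although MLT started 1.41 mmHg higher; a post hoc baseline-adjusted analysis should be shown beside it

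*Combined protocol and SAP*

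**What the plan says.** The section Study Protocol and Statistical Analysis Plan with Results describes allocation, baseline and test as follows.

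- Allocation: "38 patients were randomized to MLT and 31 patients to SLT via a random number generator protocol", and "Patients were allocated to each group without any stratification based on prior characteristics". Baseline IOP was therefore not balanced by design.
- Baseline: "Pretreatment IOP values were calculated as the average of up to three preceding visits to reduce fluctuations".
- Test: "Comparison between groups was calculated with" Student's t-test for continuous data and Fisher's exact test for categorical data. No covariate, regression or analysis of covariance is mentioned.

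The Results section then reports:

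- Baseline: "The MLT patients had a higher average starting IOP (18.26 mmHg) than the SLT group (16.85 mmHg), approaching significance", with P=0.08.
- One hour: "Both groups had very similar 1 hour posttreatment IOP, 15.15 mmHg in the MLT group and 15.65 mmHg in the SLT group".
- Follow-up intervals from week 1 to week 52: "both MLT and SLT provided comparable decreases in IOP from baseline as both an absolute measurement and a percentage decrease at all intervals".

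**The concern.** Patients who start with higher IOP tend to show larger falls, partly through regression to the mean and partly because there is more pressure to lower. Subtracting baseline removes this only if follow-up IOP rises one-for-one with baseline (b = 1). If b is below 1, the arm that starts higher shows a larger fall even when the two lasers work equally well. Here that arm is MLT.

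The reason to adjust is that baseline IOP predicts the change, not that P was near 0.05. What is at stake is the estimate behind the statement that the lasers give comparable decreases. That statement is supported by non-significant t-tests and by confidence intervals set against 3 mmHg and 20%, with one interval conceded as an exception. A non-significant test does not show comparability, so the location of the estimate and its interval matters. Both depend on how baseline is handled.

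**Working it through.** **Inputs from the documents.** Arms of 38 (MLT) and 31 (SLT); baseline 18.26 and 16.85 mmHg, P=0.08; one-hour IOP 15.15 and 15.65 mmHg; 80% power at α = 0.05 for 2.99 mmHg or 16.19%. No SD and no baseline–follow-up slope is given, so b is an assumption, shown over a range.

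**The plan's own figure.** The 80% power cannot be reproduced without an SD; it can only be solved backwards. A two-sided t-test with 38 and 31 patients has 80% power at 2.99 mmHg if the SD of change is about 4.35 mmHg. Two-sidedness and the analysed numbers are assumptions. The baseline P=0.08 gives t = 1.778 on 67 df, SE = 1.41/1.778 = 0.793, and a baseline SD of 0.793/√(1/38+1/31) ≈ 3.28 mmHg (3.22 to 3.33 for P from 0.075 to 0.085).

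**Absolute scale.** Gap = 18.26 − 16.85 = 1.41 mmHg. The adjusted difference in decrease (MLT minus SLT) equals the unadjusted difference minus (1−b) × 1.41.

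| assumed b | tilt toward MLT, mmHg | share of 2.99 |
|---|---|---|
| 0.3 | 0.7 × 1.41 = 0.99 | 33% |
| 0.5 | 0.5 × 1.41 = 0.71 | 24% |
| 0.7 | 0.3 × 1.41 = 0.42 | 14% |
| 0.8 | 0.2 × 1.41 = 0.28 | 9% |

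Averaging up to three pretreatment visits reduces noise in the baseline. That pushes b upward and makes the smaller tilts more likely.

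**Percentage scale.** The pooled baseline is (38 × 18.26 + 31 × 16.85)/69 = 17.63. With mean fall F, the expected percentage fall at baseline x is 100 × [F + (1−b)(x − 17.63)]/x. The tilt is its value at 18.26 minus its value at 16.85, in percentage points:

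| assumed b | F = 2 | F = 3 | F = 4 |
|---|---|---|---|
| 0.5 | 3.12 | 2.66 | 2.21 |
| 0.7 | 1.51 | 1.05 | 0.59 |
| 0.8 | 0.70 | 0.24 | −0.22 |

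For F = 3 these are 16%, 6% and 1.5% of 16.19%. At F = 3 the tilt is 4.3 points if b = 0.3 and −0.6 if b = 0.9. Percentage change therefore nearly cancels the imbalance only for b around 0.8; it is not an adjustment in general.

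**One hour, the only time point with both means.** Assume the stated baselines apply to the patients measured. The falls are 18.26 − 15.15 = 3.11 and 16.85 − 15.65 = 1.20, which differ by 1.91, while the one-hour IOPs differ by 0.50. The 1.41 between these two summaries is exactly the baseline gap. The adjusted difference is 0.50 + 1.41b: 0.50 at b = 0, 1.49 at b = 0.7 and 1.91 at b = 1. It favours MLT throughout.

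**Room under the 3 mmHg benchmark.** This assumes that the Results' confidence intervals are between-arm intervals. With a change SD of 4.35, the SE for all 69 patients is 4.35 × √(1/38+1/31) = 1.05 and the half-width is about 2.1 mmHg. The 24–52-week responder percentages fit denominators of 27 and 25 (8/27 = 29.6%, 10/27 = 37.0%, 9/25 = 36.0%). With those numbers the SE is 1.21 and the half-width about 2.4. The point estimate then has about 0.9 or 0.6 mmHg of room, which is of the same order as the tilts above.

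**Precision.** The residual variance under adjustment is 4.35² − (1−b)² × 3.28². Allowing for the baseline imbalance, the ratio of adjusted to change-score SE is 0.948 at b = 0.5, 0.997 at 0.7 and 1.012 at 0.8.

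**The case against.** The strongest reply is that randomisation already makes the t-test valid, that the shift is modest and its effect on the conclusion unknown, and that a supplementary table in a finished trial matters little. At b of 0.7 to 0.8 the tilt is 0.42 to 0.28 mmHg, or about 0.40 to 0.27 of the 1.05 mmHg SE. This is fair on size and rules out any claim that the result is wrong. It does not remove the case for an estimate free of a known imbalance, at the cost of one re-run.

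Four further points deserve an answer.

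- The 1.41 mmHg gap is for all patients. Data after a further intervention are excluded, and failures were unequal (23.7% MLT, 12.9% SLT), so the gap among patients analysed later may differ. This stands: every tilt above is conditional on 1.41.
- The one-hour reading is not among the intervals declared comparable, and it follows apraclonidine. This also stands. It shows that the estimate depends on the handling of baseline and says nothing about later intervals.
- The precision figures rest on back-solved SDs. This stands too. If the power statement referred to 27 and 25 patients, the change SD would be 3.77 rather than 4.35. Equal SDs at baseline and follow-up would give variance ratios of 0.75 to 0.85 for correlations of 0.5 to 0.7. A gain in precision should therefore be neither promised nor excluded.
- Comparability also rests on percentage decrease, failures and the Kaplan–Meier curve (log-rank P=0.31). Percentage decrease is tilted little only over part of the range of b. The failure and survival results do not bear on the statement about the size of the decreases.

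**Conclusion.** The concern holds. The absolute decreases are compared without adjustment for a 1.41 mmHg baseline difference, and no adjusted analysis is reported. Conditional on this sample, the comparison is tilted toward MLT by 0.28 to 0.99 mmHg for b from 0.8 down to 0.3, with the smaller values more likely; the limits are 0 at b = 1 and 1.41 at b = 0. These figures assume a common linear slope and that the all-patient gap applies at each interval.

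Whether the conclusion of comparable decreases would change is unknown, because b, the later interval means and the interval-specific gaps are not in the text. The material gives no ground for claiming a hidden SLT advantage. The benefit is an estimate that does not depend on this chance imbalance. It is an improvement that should be made, not a defect that invalidates the t-test.

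**What to change.** At each follow-up interval, fit an analysis of covariance of IOP on treatment arm and continuous pretreatment IOP, or one equivalent mixed model over all intervals. Report the adjusted MLT–SLT difference with its 95% CI.

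Label this analysis post hoc, because results are already known and only the t-test was named, and show it beside the existing comparison rather than in its place. For every interval, give the number and mean pretreatment IOP by arm of the patients who contribute, so that the reader can see the imbalance that applies there.

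The cost is a re-run of the analysis. Pretreatment IOP is already held, since every decrease is calculated from it, and no further patients or visits are needed.
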